3.4 Subject Disposition and Evaluability

3.4.1 Subject Disposition

The number of subjects screened and who failed screening will be displayed. The number and percentage of subjects who are randomized, dosed, withdrawn from the study (including reasons for withdrawal), complete the study, the number of subjects with a Week 6 remote visit performed, and the number of subjects with a remote Week 12 visit performed will be displayed for subjects 4-12 years old (inclusive) by treatment group and overall for all subjects who signed informed consent. The number and percentage of subjects in the ITT, SS, FAS, PPS, [REDACTED] will also be displayed by treatment group and overall.

The number of subjects who screened, dosed, completed the study, withdrew from the study, and the number and percentage of subjects in the ITT and SS will be summarized separately for subjects 2 to 3 years old (inclusive). The number of subjects with a Week 6 remote visit performed, and the number of subjects with a remote Week 12 visit performed will also be included.

In addition, for subjects 4-12 years old (inclusive) and separately subjects aged 2 to 3 years old (inclusive), a summary table of subjects with at least one visit affected by COVID-19 will be presented. A separate subject listing of subject visits and assessments affected by COVID 19 will be provided.

A by-subject listing of study completion information will be presented. A by-subject listing of subjects who are screen failures, and the reason for screen failure, will also be presented.

3.4.2 Protocol Deviations

The number and percent of subjects with at least one major protocol deviation and the number and percent of subjects with at least one major deviation of each deviation type will be presented by treatment group and overall for the FAS. All relevant protocol deviations will be shown in a subject listing by treatment group. Subjects with major deviations identified as exclusions from the per-protocol analysis set will be indicated in a listing. In addition, deviations related to COVID-19 will be identified in a separate listing.

A separate listing of reasons for exclusion from the Per Protocol Set for subjects ages 4-12 years old (inclusive) will also be provided.

3.5 Demographics and Baseline Characteristics

3.5.1 Demographics

All demographic and baseline characteristics data will be summarized descriptively for subjects 4-12 years old (inclusive) by treatment group and overall for the SS, FAS, and PPS. A separate summary will be provided for subjects 2-3 years old (inclusive) in the SS.

Descriptive statistics will be displayed for age at screening, age at baseline, height, weight at baseline, and body mass index (BMI). Age at screening (collected as age at time of informed consent) is recorded at the time of randomization (or enrollment for subjects aged 2 to 3 years). In addition, if the age of the subject changed between signing of informed consent and the randomization (enrollment) visit, this information is also recorded. For such cases in which the age is reported to have changed, one year is added to age at screening to determine age at baseline. For all other subjects, age at baseline is set to the age at screening. Height, weight and BMI will be summarized with the data collected at the baseline visit.

Frequencies and percentages will be tabulated for age group (randomization stratification variable: age 4 to 8 years versus age 9 to 12 years) [for subjects 4-12 years old (inclusive) only], region, gender, race, ethnicity, study center, country and history of seizures. History of seizures will be categorized as follows:

- Yes, seizure within last two years (defined as seizures within the same year or the year before informed consent)
- Yes, but no seizure within the last two years
- Yes, but unknown status in last two years
- No

- Unknown.

All demographics and baseline characteristics will be presented by subject in a data listing.

3.5.2 Medical History

All medical history conditions will be coded using the Medical Dictionary of Regulatory Activities (MedDRA, Version 22) and will be classified by MedDRA system organ class (SOC) and preferred term (PT). Medical history will be tabulated separately for subjects 4-12 years old (inclusive) and subjects 2-3 years old (inclusive) by SOC and PT for each treatment group and overall for the SS. All medical and surgical history conditions will be included in subject data listings.

3.5.3 Seizure History

Seizure history will be included in a subject data listing for subjects in the SS, sorted by age group at screening (subjects 4-12 years old (inclusive) and subjects aged 2 to 3 years old (inclusive)).

3.6 Prior and Concomitant Medications

Prior medications are defined as medications that started before first study drug administration and either stopped before or continued after first study drug administration. Concomitant medications are defined as medications that are being taken while on study drug. Medications that are ongoing on the date of the first administration of study drug will be classified as both prior and concomitant. Any medication that cannot be confirmed as stopping before the start of study drug will be classified as both a prior and a concomitant medication.

Partial medication dates will be imputed with maximum conservatism when determining if a medication is concomitant. If the onset date is missing or partial, the date will be compared as far as possible with the date of first dose of study medication. If no month is present and it is in the same year as the date of first treatment, or the year and month are the same as the first treatment date, the onset date will be imputed as the date of first treatment. Otherwise it will be imputed as 01 January in the available year, or the first day of the month and year available. End dates will be imputed as 31 December in the available year, or the last day of the available month and year collected. The imputed start date must be less than or equal to the imputed stop date.

All medications will be coded with the WHO Drug Dictionary (WHO-DD B3 format, March 2019). Prior and concomitant medications will be summarized separately and the number and percentage of subjects in each treatment group who took at least one

prior (concomitant) medication as well as the number and percentage of subjects who took each type of medication will be summarized separately for subjects 4-12 years old (inclusive) and subjects 2-3 years old (inclusive) by Anatomic Therapeutic Class (ATC) Level 2, ATC Level 4, and Preferred Term (PT) for the SS. If a subject has more than one occurrence of the same PT, then the PT will be counted only once for that subject. Similarly, if a subject has more than one PT within ATC Level 4 or ATC Level 4 within ATC Level 2, then the subject will be counted only once in that ATC Level 4 or ATC Level 2.

3.6.1 Non-Benzodiazepine Concomitant Medication

A separate summary of non-benzodiazepine concomitant medications indicated for seizure therapy will also be presented. Non-benzodiazepine medications will be classified based on WHO-DD ATC Level 2, ATC Level 4 and PT, as appropriate, prior to unblinding at database lock. Full details of the classification will be provided in the analysis data specifications. The number and percentage of subjects in each treatment group who took at least one non-benzodiazepine medication for seizure therapy, only one non-benzodiazepine medication for seizure therapy, two non-benzodiazepine medications for seizure therapy, three or more non-benzodiazepine medications for seizure therapy, as well as the number and percentage of subjects who took each type of non-benzodiazepine medication will be summarized separately for subjects 4-12 years old (inclusive) and subjects 2-3 years old (inclusive) by Anatomic Therapeutic Class (ATC) Level 2, ATC Level 4, and Preferred Term (PT) for the SS. A similar summary will be presented for non-benzodiazepines indicated for sleep. Medications with an indication for seizure therapy and with an indication for sleep will also be classified prior to unblinding at database lock and detailed in the analysis data specifications.

3.6.2 Benzodiazepine Concomitant Medication

A summary of benzodiazepine concomitant medications by dose frequency (As Needed, Immediately (STAT), Regularly, Unknown, Other) will also be presented. Benzodiazepine medications will be classified based on WHO-DD ATC Level 2, ATC Level 4 and PT, as appropriate, prior to unblinding at database lock. Full details of the classification will be provided in the analysis data specifications. For each dose frequency, the number and percentage of subjects in each treatment group who took at least one benzodiazepine medication, only one benzodiazepine medication, two benzodiazepine medications, three or more benzodiazepine medications, as well as the number and percentage of subjects who took each type of benzodiazepine medication will be summarized separately for subjects 4-12 years old (inclusive) and subjects 2-3 years old (inclusive) by ATC Level 2, ATC Level 4, and PT for the SS. A similar summary will be presented for benzodiazepines indicated for seizure therapy

by dose frequency. In addition, a summary of benzodiazepines indicated for non-seizure therapy by dose frequency will also be presented.

3.6.3 Most Common Concomitant Medication

A table of the most common concomitant medications for subjects aged 4 to 12 years old (inclusive) and separately for subjects 2-3 years old (inclusive) will be presented. The most common concomitant medications are those with an incidence $\geq 10\%$ overall. The number and percentage of subjects in each treatment group who took at least one of the most common concomitant medications as well as the number and percentage of subjects who took each type of medication will be summarized by ATC Level 2 for the SS.

All prior and concomitant medication data will be listed for subjects in the ITT, including the WHO Drug ATC 2 and ATC 4 class, PT term, the investigators verbatim description and the classification as prior, concomitant or both. Medications will be sorted by medication start date within subject. Rescue medications and anti-epileptic medications will be flagged. Separate listings will be provided for benzodiazepine and non-benzodiazepine medications.

Concomitant procedures will be presented in subject listings for subjects in the ITT.

3.7 Treatment Exposure and Compliance

3.7.1 Exposure to Study Treatment

Treatment duration or days on treatment (defined as Last dose date – First dose date + 1) will be described for the SS, separately for subjects aged 2 to 3 years old (inclusive) and 4 to 12 years old (inclusive), and for the FAS using summary statistics. Additionally, study drug administration method to be used throughout the study (capsule or powder) as recorded at baseline and the number of subjects with at least one missed dose will also be presented. A missed dose is defined as at least one day when study medication was not administered as reported on the medication diary, with a missing diary day considered as dose not administered. Treatment duration frequencies will be summarized for the intervals 1 to ≤ 5 days, 6 to ≤ 11 , 12 to ≤ 42 days, 43 to ≤ 70 , 71 to ≤ 84 days, 85 days or more by treatment group and overall. Furthermore, treatment duration frequencies will also be summarized for the same intervals described above by weight band at screening (9 to 16.99 kg, 17 to 24.99 kg, 25 to 34.99 kg, 35 to 44.99 kg, and 45 to 64.99 kg).

3.7.2 Compliance to Protocol Intended Dose

Treatment compliance will be summarized for the SS and FAS for subjects aged 4 to 12 years old (inclusive) and for the SS for subjects 2-3 years old (inclusive), by

treatment group over the entire treatment period. Study drug is dispensed at Baseline and Week 6. Compliance rates during the treatment period will be derived using the following formula:

$100 * ((\text{Total number of capsules taken}) / (\text{Expected number of capsules to be taken}))$,
where “Total number of capsules taken” will be derived separately for the intervals Baseline to Week 6 and for Week 6 to Week 12/EOT and is calculated as the total number of capsules dispensed minus the total number of capsules returned from the corresponding drug kit. The total number of capsules taken on study will be derived as the sum of the total capsules taken from the two intervals. Total number of capsules taken will be missing for an interval based on drug dispensation if drug kit is dispensed but not returned or is lost. In such cases, total number of capsules taken for the interval will be derived based on the study medication diary, where the “Total number of capsules taken” will be derived as the sum of the total number of capsules reported to have been taken each study day in the interval, with missing diary dates treated as 0 capsules taken. Complete derivation details will be provided in the ADaM specifications.

Expected number of capsules to be taken is based on the date of first study medication dose and the date of last study medication dose and the subject’s weight range band at screening that determines the number of capsules expected to be taken at each study week, following the expected daily dosing and titration schedule (see protocol section 5.1)

Descriptive statistics will be displayed for total number of capsules taken, expected number of capsules taken, and compliance rate. Compliance rates will also be presented using frequency and percentages for the categories 0% to <20%, 20% to 40%, 40% to <60%, 60% to <80%, 80% to <=100%, >100% to ≤120%, or >120% by treatment group and overall.

All study drug exposure and compliance information will be presented in subject listings. All study drug titrations, study drug accountability, study medication taken daily diary information, and study medication overdoses will also be presented in by-subject listings.

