Dosing will be initiated at the starting dose for the first 5 days. On Day 6, tolerability will be assessed by the investigator. If there are no tolerability concerns (e.g., excessive somnolence, dizziness, vomiting, negative behavior changes) and no AE related to the study drug has been observed since Day 1 by the LAR/caregiver or the investigator, then the dose of OV101 will be increased to the maintenance dose for the duration of the study. The maintenance dose identified at screening will remain consistent throughout the study. If tolerability concerns are observed on Day 6, the subject will discontinue study drug.

[figure not shown]
The subject's maintenance dose for the duration of the study will be set based on the subject's weight at the screening visit, and the subject should continue taking the maintenance dose after the Day 6 assessment until the EOS. Tolerability will again be assessed during the Day 11 phone call while the subject is taking the maintenance dose. The investigator may initiate down-titration on Day 11 by 1 capsule (Table 2) based on investigator assessments of tolerability and AEs, or medical necessity. If down-titration is initiated, then the investigator should reassess tolerability with the modified dose regimen within 3 days of the dosing change. No further changes in dose regimen should be made after Day 15.

[figure not shown]
If tolerability is not acceptable at any other time during the 12 weeks of treatment, the investigator should discuss the situation with the medical monitor or his/her delegate. Any intolerability must be documented as an AE. The daily dose may not be lower for any subject than the reduced maintenance dose indicated in Table 2. If a subject cannot tolerate the reduced maintenance dose, that subject must discontinue treatment. Any dose adjustments or changes in dosing must be documented in the electronic case report form and supporting rationale must be documented in the medical record or other appropriate source document.

Sample Size:

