7.7 Exposure and Compliance

Treatment compliance will be summarized by treatment group over the entire treatment period. Compliance rates during the treatment period will be derived using the following formula:

$100 \times (\text{Total number of capsules dispensed} - \text{Total number of capsules returned}) / (\text{Expected number of capsules})$

The expected number of capsules to be taken is based on the date of first study drug dose and the date of last study drug dose, the subject's weight range band at screening that determines the number of capsules expected each study week, following the titration schedule (Section 5.1), and any dose down-titrations (Section 5.2.1). Compliance rates will be presented for the SS using summary statistics and percentage for the frequency distributions (0% to <20%, 20% to 40%, 40% to <60%, 60% to <80%, 80% to <100%, 100% to $\leq 120\%$) by treatment group and overall.

Data for subjects 2 to 3 years old (inclusive) will be presented separately in listings.

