3.1.8 Analysis Visit Windows

Visit windows for study conduct are specified in Table 1: Schedule of Activities. Unless otherwise specified, the following analysis visit rules will be implemented for all endpoints [REDACTED] and seizure diary (see sections 3.8.3, 3.8.4, and 3.9.6 for analysis visit window computations). For all unscheduled visits and end of treatment (EOT) visits from subjects discontinuing treatment early (before Week 12), assessments will be mapped according to the analysis visit windows in Table 2 for primary summarization and analysis. If the visit does not fall within any of the analysis visit windows, then the visit will be considered missing at the specified time point for analysis purposes.

Table 2: Nominal (Targeted) Time Points and Analysis Visit Windows

Assessment	Nominal (Targeted) Time Point	Analysis Visit Window (Interval in Study Days)
Baseline Assessments	Study Day 1	≤ Day 1
Phone/Titration (Day 6)	Study Day 6	>Day 1 - ≤Day 8
Phone/Titration (Day 11)	Study Day 11	≥Day 9 - ≤Day 21
Week 6 (Study Day 43)	Study Day 43	≥Day 22 - ≤Day 64
Week 12 (Study Day 85)	Study Day 85	≥Day 65 - ≤Day 92
Week 14 (Study Day 99)	Study Day 99	≥Day 93

After mapping the data from unscheduled and end of treatment (EOT) visits from subjects discontinuing treatment early to the nominal time point, the following rules will apply if multiple records are available within a single analysis visit window unless otherwise specified for a particular analysis:

- If a record exists for the nominal time point, that record will be selected for analysis.
- If a record for the nominal time point does not exist and multiple records are available within a single analysis visit window,
 - The record closest to the planned assessment day will be selected for analysis
 - If 2 records are equidistant from the target day, then the earliest record will be selected (does not apply to the Week 12 or 14 visits).
- If a subject has no record in an analysis window, the subject will be considered missing at that time point.

For the primary and key secondary objectives, a supportive analysis will be conducted in which CGI-I-AS assessments from unscheduled visits and end of treatment (EOT) visits from subjects discontinuing treatment early (before Week 12) will be mapped according to the analysis visit windows in Table 3.

Table 3: Nominal (Targeted) Time Points and Alternative Analysis Visit Windows

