3.2 Analysis Populations and Subgroups

3.2.1 Definition of Analysis Populations

The following analysis sets, with the exception of the Intent-to-treat and Safety Set, will only include subjects 4 to 12 years old (inclusive) at screening. The baseline and safety analyses for subjects 2 to 3 years old (inclusive) at screening will be conducted separately.

Intent-to-Treat Analysis Set

The intent-to-treat set (ITT) will consist of all subjects who are randomized (subjects aged 4 to 12 years old (inclusive) or enrolled (subjects aged 2 to 3 years old (inclusive) and meet all inclusion and exclusion criteria), whether or not study drug is received. Subjects aged 4 to 12 years old (inclusive) will be analyzed according to their randomized treatment.

Full Analysis Set

The full analysis set (FAS) will include all subjects aged 4 to 12 years old (inclusive) who are randomized, receive at least 1 dose of study drug, and have at least 1 post-baseline assessment of the primary efficacy endpoint. The FAS will be used for efficacy analyses based on the randomized treatment for each subject.

Per Protocol Set

The per protocol set (PPS) is a subset of the FAS that includes subjects who complete the Week 12 CGI-I-AS assessment (with appropriate visit mapping as shown in Table 2) and have no major protocol deviations that are deemed to impact efficacy. These violations include but are not limited to violations of inclusion/exclusion criteria deemed to impact efficacy, inadequate study drug compliance over the dosing period as determined from the dosing information in the eCRF, usage of prohibited concomitant medications, and incorrect randomization. Additionally, other relevant protocol deviations, such as early termination or interruption of treatment, may be identified for review.

Prior to database lock and unblinding, there will be a meeting to review all protocol deviations to determine PPS exclusions. The threshold for percent compliance that would be considered inadequate and would result in exclusion from the PPS will also be determined in this meeting following review of the relevant compliance

information. The PPS will be used for efficacy analyses based on the randomized treatment for each subject.

Safety Set

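### SAP 3.7.2 leaves permitted down-titration out of the expected capsule count, so compliance is understated for a fully adherent child on the reduced dose

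*SAP*

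**What the plan says.** Both documents compute compliance as capsules dispensed minus capsules returned, divided by capsules expected. They differ in the denominator.

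- **Protocol 7.7** builds the expected count from the first and last dose dates and the screening weight band, "following the titration schedule (Section 5.1), and any dose down-titrations (Section 5.2.1".
- **SAP 3.7.2** uses the same dates and weight band, "following the expected daily dosing and titration schedule (see protocol section 5.1". It has no term for down-titration and no reference to Section 5.2.1.

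Down-titration is part of the permitted regimen. The protocol synopsis states: "The investigator may initiate down-titration on Day 11 by 1 capsule", to the level in its Table 2, and then: "No further changes in dose regimen should be made after Day 15". A child who is reduced therefore stays on the lower count for most of the treatment period.

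The compliance rate is tabulated by arm for the safety set (SS) and the FAS. Compliance also bears on the PPS: SAP 3.2.1 lists among the grounds for exclusion "inadequate study drug compliance over the dosing period as determined from the dosing information in the eCRF". The threshold is not fixed. It is to be set, after review of compliance data, at a meeting held before database lock and unblinding.

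**The concern.** Compliance should measure whether the child took what was prescribed. If the investigator has lowered the prescription as the protocol allows, the expected count has to fall with it. Otherwise a sanctioned dose change is recorded as missed capsules.

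Two outputs are exposed. The first is the by-arm compliance summary, which would be too low for every reduced child. The second is the PPS review, where the same figures may inform both the choice of cut-off and the list of children below it.

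The difference is also unexplained. Protocol 7.1 expects changes to the analysis methods, with their justification, to be described in the SAP. The SAP introduction says its methods are based on protocol Section 7.

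**Working it through.** The documents give no compliance figure or threshold to reproduce, so the check is direct arithmetic for a child who misses nothing.

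**Inputs**

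- Starting dose on Days 1-5, maintenance from Day 6 (protocol synopsis: "Dosing will be initiated at the starting dose for the first 5 days").
- D, first day on the reduced dose: Day 11 to Day 15, from the synopsis limits on regimen changes.
- L, last dose day: 84 or 85, from 12 weeks of treatment and the SAP 3.1.8 target of "Week 12 (Study Day 85").
- Size of the reduction: 1 capsule (protocol synopsis).
- m, maintenance capsules per dose: **assumed** 2 to 6. s, starting capsules per dose: **assumed** 1 to m. The dosing tables are not visible.

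**Formulas**

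- Expected under the SAP = 5s + (L − 5)m
- Taken = 5s + (D − 6)m + (L − D + 1)(m − 1)
- Compliance = 100 × taken / expected

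Expected minus taken is always L − D + 1 capsules, one for each day on the reduced dose. Under protocol 7.7, expected equals taken, so compliance is 100%.

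**Worked case** (m = 3, s = 2, L = 85)

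- D = 11: expected = 10 + 240 = 250; taken = 10 + 15 + 150 = 175; compliance = 70.0%.
- D = 15: expected = 250; taken = 10 + 27 + 142 = 179; compliance = 71.6%.

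**Full range over s and L**

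| Maintenance capsules (assumed) | Reduced from Day 11 | Reduced from Day 15 | Protocol 7.7 rule |
|---|---|---|---|
| 2 | 54.5-56.0% | 57.0-58.3% | 100% |
| 3 | 69.4-70.6% | 71.0-72.2% | 100% |
| 4 | 76.9-78.0% | 78.2-79.2% | 100% |
| 5 | 81.5-82.4% | 82.5-83.3% | 100% |
| 6 | 84.5-85.3% | 85.4-86.1% | 100% |

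The understatement is 13.9 to 45.5 percentage points. In the SAP's own tabulation bands, the 2-capsule child falls in 40% to <60% and the 3- and 4-capsule children in 60% to <80%. Only with 5 or 6 capsules does the child reach the 80% to 100% band.

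**Number of children affected.** No down-titration rate is given, so this is illustration only, with about 45 children per arm (SAP 2.2.1). Assumed rates of 5% in both arms give 45 × (0.05 − 0.05) = 0 excess on OV101. Rates of 10% against 5% give 45 × 0.05 = 2.25. Rates of 20% against 5% give 45 × 0.15 = 6.75.

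**The case against.** **The SAP wording may already cover it.** A permitted reduced dose could be called expected daily dosing, and protocol 5.2.1 mentions down-titration under the heading of dose titration. SAP 3.7.2 also leaves derivation details to ADaM specifications that are not in the documents. This is weak. Protocol 7.7 names the schedule and down-titrations as separate items with separate references, and the SAP keeps only the first. An individual investigator's decision cannot be derived from weight band and dates. The section the SAP cites, 5.1, covers randomization. Programming specifications should implement the SAP, not repair it.

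**The SAP was written for another protocol version.** It cites version 4.0, and the protocol supplied is version 6.0. Whether version 4.0 had the clause cannot be seen. The current protocol has it, so the two need aligning either way.

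**A reader might infer that these children are classed as non-compliant and dropped from the PPS.** The documents do not support that. No threshold exists; the 80% band edge is for tabulation only. SAP 3.2.1 points to eCRF dosing information rather than to the 3.7.2 rate by name. Titration steps are in the eCRF, SAP 3.7.2 lists them by subject, and the review is held before unblinding. A permitted reduction is not itself a deviation. This objection stands.

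**A reader might also infer that exclusions would fall more heavily on OV101.** Down-titration is driven by tolerability, so an imbalance is plausible. But no rate by arm is given, and both arms follow the same titration rules. Protocol Section 1 reports similar adverse event incidence and severity across the Phase 2 groups, with adverse event discontinuations of 1 on placebo, 0 on once-daily and 3 on twice-daily OV101. Children with tolerability concerns on Day 6 stop study drug under the protocol, so some would leave before Day 11. This objection also stands.

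**The PPS is one check among several.** SAP 3.1.3 treats it as a sensitivity analysis only. SAP 3.8.1 adds a Week 12 ANOVA, an exact Wilcoxon test and alternative visit mappings. This is correct and limits the consequence.

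**Conclusion.** Wrong as written; minor severity. Taken literally, SAP 3.7.2 gives a fully adherent child on the permitted reduced dose a compliance of roughly 55% to 86%, where the protocol's rule gives 100%. The direction of the error is certain for any such child. Its size rests on the assumed 2 to 6 maintenance capsules, a reduction starting between Day 11 and Day 15, and a last dose on Day 84 or 85.

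The SS and FAS compliance tables are misstated to the extent that children are down-titrated, whether or not the arms differ. The PPS threshold and exclusions can be distorted if the review relies on the computed rate, but exclusion does not follow automatically. An arm imbalance cannot be established from the documents. The FAS primary analysis, the key secondary tests and the control of type I error do not use compliance and are unaffected.

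**What to change.** In SAP 3.7.2, restore the protocol 7.7 rule: expected capsules follow the titration schedule and, from the date recorded in the eCRF, any protocol-permitted down-titration. Change the cross-reference from protocol Section 5.1 to Section 5.2.1, where dose titration is described. Protocol 7.7 carries the same Section 5.1 reference and can be corrected when it is next amended. Make the SAP change before the PPS review meeting, so that the threshold is chosen from correct figures.

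The cost is one clause, one reference and a small change to the derivation program. Titration steps and dose changes are already recorded in the eCRF, so no new data are needed.
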